8.3.2. Laboratory Tests

Absolute values and changes from baseline will be summarized at each assessment time point by treatment group for the following laboratory tests parameters.

Laboratory Test	Parameters
-----------------	------------

Hematology	RBC, Hemoglobin, Hematocrit, MCHC, WBC, Platelet, Neutrophils, Lymphocytes, Monocytes, Basophils, Eosinophils
Biochemistry	AST, ALT, ALP, LDH, Gamma-GTP, Total protein, Albumin, Total cholesterol, Total bilirubin, BUN, Serum creatinine, eGFR, Na, K, Cl, Ca, HCO ₃ , Uric acid, Triglycerides, BAP, Inorganic phosphorus, CPK, CRP
Urinalysis	pH, Specific gravity, Creatinine, Phosphate (Qualitative value) : Glucose, Protein, Occult blood, Bilirubin, Nitrite, WBC, Sediment WBC, Hyaline casts, Epithelial cells, Bacteria, Yeast, Ketones

Shift table of clinically relevant categories will be presented for the following laboratory tests parameters.

All data will be listed.

8.3.3. Vital Signs

Absolute values and changes from baseline will be summarized at each assessment time point by treatment group for the following parameters.

- Systolic Blood Pressure (mmHg)
- Diastolic Blood Pressure (mmHg)
- Pulse Rate (bpm)
- Body Temperature(°C)

The percentage of subjects with vital signs pre-defined limit will be summarized.

All data will be listed.

8.3.3.1. Assessment of Orthostatic Blood Pressure with standing value minus supine value

Absolute values and changes from baseline will be summarized at each assessment time point by treatment group for the following parameters.

- Systolic blood pressure 1 minute after standing
- Diastolic blood pressure 1 minute after standing
- Pulse rate 1 minute after standing
- Systolic blood pressure 3 minute after standing
- Diastolic blood pressure 3 minute after standing
- Pulse rate 3 minute after standing

8.3.4. ECGs

Absolute values and changes from baseline will be summarized at each assessment time point by treatment group for the following parameters.

- Heart Rate (bpm)

- PR (msec)
- RR (msec)
- QRS (msec)
- QT (msec)
- QTcF (msec)

The percentage of subjects with ECG values outside pre-defined limit will be summarized.

All data will be listed.

8.3.5. Physical Examinations

Physical examination will be listed for the following parameters.

- General Appearance
- Neurological
- Eyes
- Ears, nose, throat
- Cardiovascular
- Respiratory
- Abdominal
- Hepatic
- Gastrointestinal
- Musculoskeletal
- Dermatological

8.3.6. Bone density

Bone density will be summarized and listed for the following parameters.

- YAM(%) and T-score
 - Femoral neck
 - Total hip
 - Lumber Vertebra

8.3.7. JOA score

JOA score will be listed. Spaghetti plots including all available follow-up data after baseline will be presented by treatment group and JR joint and the corresponding to joint.

8.3.8. Radiograph

Adjudicated Arthropathy

Overall summary for adjudicated arthropathy will be conducted.

The following summaries for adjudicated arthropathy also will be conducted.

- Subtype of adjudicated arthropathy
- Subtype of adjudicated arthropathy meeting destructive arthropathy

- Incidence rate of adjudicated arthropathy
- Time to first event of adjudicated arthropathy

As regards time to first event adjudicated arthropathy, cox regression model will be used for descriptively comparing each treatment group to placebo by obtaining hazard ratio estimates along with 95% confidence intervals.

Each of the summaries will be done by treatment group and combined MT-5547.

All data will be listed.

Joint Space Width

The following summaries for joint space width will be conducted.

- Non arthropathy adjudication joint with adjudicated arthropathy
- All joint with non adjudicated arthropathy subjects

Joint space width for AA will be summarized by treatment group and combined MT-5547. All data will be listed. Each of the summaries will be done by treatment group and combined MT-5547.

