- (39) Presence or history of human immunodeficiency virus (HIV), hepatitis B virus (HBV), or hepatitis C virus (HCV) infection, except that patients with a history of hepatitis B are eligible if negative for HBs antigen and positive for HBs antibodies, and patients with a history of hepatitis C are eligible if the hepatitis C virus RNA test results are negative.
- (40) Use of an anti-NGF antibody in the past, or apparent hypersensitivity or intolerance to anti-NGF antibodies.
- (41) Women who are pregnant, breastfeeding, or may be pregnant (positive serum pregnancy test) women of childbearing potential for whom pregnancy test results are not available, or women of childbearing potential, or men with female partners of childbearing potential, who are unwilling to use contraception during the study and for 20 weeks after the last dose of investigational drug or comparative drug.
- (42) Patients otherwise judged by the (sub)investigator to be unsuitable for the study.

Exclusion Criteria at Baseline

- (43) Autonomic neuropathy diagnosed in the assessment of autonomic nerve symptoms performed at baseline (for details, see “9.2.4.1.7 Autonomic Nerve Assessments”).
- (44) Orthostatic hypotension found at the orthostatic hypotension assessments performed at baseline (for details, see “9.2.4.1.8 Standing Blood Pressure Assessment”).
- (45) Resting heart rate of <50 bpm or >100 bpm at baseline.
- (46) Use of a prohibited concomitant medication during the pre-treatment observation period (see Attachment 4, “List of Prohibited Concomitant Medications”).
- (47) Women who may be pregnant based on a positive urine pregnancy test result, and women of childbearing potential for whom no pregnancy test results are available.
- (48) Presence of adjudicated arthropathy by the central rater based on the MRI tests performed at screening.
- (49) Patients who forgot to input their NRS data (average pain on walking in the evaluated joint over 1 day) 4 or more times during the IVRS training in the pre-treatment observation period.
- (50) Patients otherwise judged by the (sub)investigator to be unsuitable for the study (a check will be performed of the exclusion criteria that were checked in the screening period and pre-treatment observation period as well to ensure that there has been no change to these findings).

4. Explanation and Consent

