8.3. Safety Assessments

Safety assessments will be made on the SAF population.

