8.3.1. Adverse Events

Overall summary of TEAEs / Post-treatment AEs for the following will be conducted.

- Subjects with at least one AE
- Subjects with at least one adverse drug reaction
- Subjects with at least one SAE
- Subjects with at least one serious adverse drug reaction
- Subjects with at least one AESI
- Subjects with at least one severe AE
- Subjects with at least one AE leading to discontinuation of study drug
- Subjects with AE leading to death

The following summaries also will be conducted.

- TEAEs / Post-treatment AEs by SOC and PT
- TEAEs / Post-treatment AEs related to drug reactions by SOC and PT
- TEAESI / Post-treatment AESI by SOC and PT
- TESAEs / Post-treatment SAEs by SOC and PT
- TESAEs related to drug reactions by SOC and PT
- TEAEs leading to discontinuation of study drug by SOC and PT

- TEAEs / Post-treatment AEs by SOC, PT and severity
- TEAEs related to drug reactions by SOC, PT and severity
- TEAEs by SOC, PT and relationship to study drug
- TESAEs by SOC, PT and relationship to study drug
- Identified TEAEs / Post-Treatment AEs by SMQ, HLGT, HLT and PT

Each of the summaries will be done by treatment group and combined MT-5547 at the subject level - multiple occurrences of the same event within a subject will be counted once in the summaries by SOC and PT; multiple occurrences of the same event within a subject will be counted once in the maximum severity category (severe > moderate > mild) and/or maximum drug relationship category (reasonable possibility/no reasonable possibility) and/or the earliest duration.

The following will be listed.

- AE
- AESI
- AE leading to discontinuation of study drug
- SAE
- Death
- Joint replacements

adjudicated arthropathy

The number and percentage of patients with images requiring adjudicated arthropathy as well as the number and percentage of those patients with confirmed adjudicated arthropathy including all available follow-up data after baseline will be summarized by treatment group and combined MT-5547. Subtypes of AAs and outcomes of AAs will also be summarized. Time to event with AA will be analyzed using Kaplan-Meir approach and will be plotted by treatment group. Cox regression model will be used for descriptively comparing each treatment group to placebo by obtaining hazard ratio estimates along with 95% confidence intervals.

Incidence of AA will be summarized by treatment group and combined MT-5547.

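### The Week 68 SAP summarises joint space width only within groups defined by post-randomisation arthropathy status, so no planned table compares the randomised arms on this measure

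*SAP*

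**What the plan says.** Joint space width is specified in one place, section 8.3.8 (Radiograph) of the Week 68 SAP. Two summaries are listed: "Non arthropathy adjudication joint with adjudicated arthropathy" and "All joint with non adjudicated arthropathy subjects". The text then adds: "Joint space width for AA will be summarized by treatment group and combined MT-5547". It also says that all data will be listed and that the summaries are by treatment group and combined MT-5547.

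Section 8.3.8 does not mention change from baseline for joint space width. Visits have to be taken from the radiology windows in section 7.2 (baseline, Weeks 16, 48 and 68) and the radiograph column in section 9.3. Section 8.3 sets the population: "Safety assessments will be made on the SAF population".

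AA itself is analysed as an outcome. Section 8.3.1 says that patients with "confirmed adjudicated arthropathy including all available follow-up data after baseline will be summarized by treatment group and combined MT-5547". For time to first AA, section 8.3.8 says that a "cox regression model will be used for descriptively comparing each treatment group to placebo by obtaining hazard ratio estimates along with 95% confidence intervals".

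**The concern.** A comparison between arms is protected by randomisation only if the patients or joints compared are not chosen on something that treatment can change. All three groups here are chosen on AA. Protocol 11.2.1 includes rapidly progressive osteoarthritis types 1 and 2 among the arthropathies monitored, so AA is plausibly linked to the narrowing being measured. If the drug moves some fast-narrowing joints into the AA category, the joints left in the other groups are a different selection in each arm.

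Joint structure is a leading safety question for this product. Chapter 1 of the protocol reports that the two higher-dose arms were stopped after an overseas study showed imbalances that included time to total joint replacement and arthralgia. The table of patients without AA is probably the largest of the three, assuming AA is uncommon. It is the one most likely to be read as showing whether the drug affects joint space.

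**Working it through.** **1. Is AA a post-randomisation variable?** Yes. Protocol 3.3 excludes a presence or history of arthropathy confirmed by imaging (criterion 17) and also "Presence of adjudicated arthropathy by the central rater based on the MRI tests performed at screening" (criterion 48). AA in the analysis therefore arises during the study, and SAP 8.3.1 and 8.3.8 count it after baseline and compare it with placebo.

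**2. Which joints does each summary hold?**

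| Summary | Patients | Joints | Conditioned on AA? |
|---|---|---|---|
| First bullet | with AA | those not adjudicated | yes |
| Second bullet | without AA | all | yes |
| Later sentence on AA | unclear, probably with AA | unclear, probably adjudicated joints | yes |
| All joints by arm | all SAF | all | not planned |

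The later sentence has two readings. If it means the adjudicated joints, the three summaries together cover every joint. If it only introduces the two bullets, the adjudicated joints appear in the listing alone.

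**3. What can the table of patients without AA miss?** The documents give no mean, SD or AA rate for joint space width, so there is no plan figure to reproduce and every input here is assumed. Take one value per patient, with:
- p = share with AA (pT on active, pC on placebo)
- d0 = mean change without AA, first taken as −0.1 mm in both arms
- dA = mean change with AA

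Arm mean = (1 − p)·d0 + p·dA, so the all-patient difference = (pT − pC)·(dA − d0). The difference among patients without AA is 0 by construction.

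| pC | pT | dA (mm) | Arithmetic | All-patient difference (mm) |
|---|---|---|---|---|
| 2% | 2% | −2.0 | 0.00 × (−1.9) | 0 |
| 1% | 2% | −0.5 | 0.01 × (−0.4) | −0.004 |
| 1% | 5% | −1.0 | 0.04 × (−0.9) | −0.036 |
| 2% | 10% | −2.0 | 0.08 × (−1.9) | −0.152 |
| 0% | 10% | −2.0 | 0.10 × (−1.9) | −0.190 |

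**4. Is the direction fixed?** No. If patients without AA change by e more on active drug than on placebo, the all-patient difference becomes (1 − pT)·e + (pT − pC)·(dA − d0). In the third row, e = 0.036/0.95 = +0.038 mm would cancel it.

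**5. Could such a difference be seen?** Assume an SD of 0.3 to 0.8 mm for the change, and the planned 182 patients each on 1 mg q4w and placebo. The standard error is SD × √(2/182), which is 0.031 to 0.084 mm. A difference of 0.036 mm is then about 0.4 to 1.1 standard errors, and 0.19 mm about 2.3 to 6.

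**The case against.** A reader might infer that the worst narrowing is removed from view. The text does not support that. On its natural reading, the sentence after the two bullets gives a by-arm summary of the affected joints, and every value is listed. On that reading, an all-joint mean could be rebuilt from the n and mean that section 6.1 requires. The harm in the illustration is a difference in AA incidence, and the plan measures that directly: counts, subtypes, incidence rates, Kaplan-Meier curves, a Cox model against placebo, and joint replacement in 8.3.13. The zero among patients without AA is also the true answer for those patients under the assumptions made. Joint space width is descriptive, falls under imaging tests rather than being a named endpoint, and the Week 68 SAP does no formal testing.

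An all-joint mean has weaknesses of its own. It dilutes rare severe loss, and it would again lose the worst joints if replaced joints were dropped without a rule.

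Most of this stands, and it limits the point to a gap in a descriptive safety table. It does not close the gap. A mean within AA cases shows how bad the cases are, not how the arms differ overall. Rebuilding the total depends on the favourable reading of an ambiguous sentence, and it gives no standard error that allows for several joints per patient.

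**Conclusion.** The point holds in limited form. Every joint space width summary is conditioned on AA status, which arises after randomisation, and none compares the randomised groups. The scope of the AA summary is unclear. The table of patients without AA understates an arm difference if AA is more frequent on active drug, AA joints narrow more, and the remaining joints show no opposite difference.

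It may be tempting to conclude that the direction is certain whenever AA joints narrow more. It is not: with equal AA rates the effect is zero, and an opposite difference in the other joints can cancel it. The range of 0 to 0.19 mm rests wholly on assumed AA shares (0 to 2% placebo, 2 to 10% active) and assumed losses (0.1 mm without AA, 0.5 to 2.0 mm with it). The primary efficacy result and the AA incidence comparisons are unaffected.

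**What to change.** Add one descriptive table to section 8.3.8: joint space width and its change from baseline at Weeks 16, 48 and 68, using the radiology windows in 7.2. Include all knees and hips with a baseline film, show shoulders separately, and use the SAF by arm and combined, regardless of adjudication. Three details need stating:

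- Several joints per patient: use patient-level means, or a model that allows for the clustering.
- Replaced or unmeasurable joints: for example, use the last film before replacement, and report the number of joints excluded by arm.
- The AA summary: say that it means the adjudicated joints.

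Keep the AA-based summaries as supplementary breakdowns. Protocol 9.2.4.1.11 already schedules X-rays of both knees, hips and shoulders at screening and Weeks 16, 48 and 68, with central assessment. The cost is therefore one extra table and a few lines of text. Because that table dilutes rare severe narrowing, it should sit beside the AA incidence analyses and not replace them.

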8.3.9. Injection Site Assessments

Injection Site Assessments will be summarized at each assessment time point by treatment group. All data will be listed.

8.3.10. Autonomic Symptoms Questionnaire

Absolute values and changes from baseline will be summarized at each assessment time point by treatment group for the following tests.

- total symptoms score
- total symptom impact scores

All data will be listed.

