9.2.4.1.7 Assessment of Autonomic Nervous Symptoms

The (sub)investigator or a study support staff member will ask the subject to fill out Attachment 11, "Survey of Autonomic Symptoms," at screening, baseline, Weeks 4, 8, 12, 16, 20, 24, 28, 32, 36, 40, 44, 48, 52, and 68, and at treatment period discontinuation or post-treatment observation period discontinuation, and will recover said attachment after it has been filled out by the subject. The (sub)investigator will use the survey of autonomic symptoms that has been filled out by the subject to assess the subject's signs and symptoms of autonomic nervous disorders and will record the subject's symptom score and impact score in the case report form.

The symptom scores will be assessed using the following 2 categories (12 items for males and 11 items for females).

1. Yes
2. No

The impact scores will be assessed using the following 5 categories.

1. Not at all
2. A little
3. Some
4. A moderate amount
5. A lot

If the total symptom score at screening and at baseline is 4 or more or the total impact score at screening is 12 or more, the (sub)investigator will evaluate the autonomic symptoms of the subject and determine whether or not the subject should participate in the study ("3.3 Exclusion Criteria, (24)). After the start of investigational drug administration, the (sub)investigator will assess the signs, symptoms, and worsening in the subject's autonomic symptoms, and will, taking into account other outcome measures, confirm whether or not the subject has a sympathetic nervous disorder (see "11.2.2 Monitoring of Sympathetic Nerve Disorders").

These assessments should be performed by the same (sub)investigator throughout the term of the study. If the (sub)investigator determines that a specialist (a neurologist or a circulatory medicine specialist) needs to perform the sympathetic nervous disorder assessment, then the (sub)investigator will consult a specialist.

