13.3.3 Safety

Adverse events that occur in the treatment period will be tabulated as treatment-emergent adverse events (TEAEs). TEAEs are defined as AEs that developed or worsened during the treatment period. The numbers and proportions of subjects with TEAEs, TEAEs that are causally related to study treatment, TEAEs that result in study treatment discontinuation, serious TEAEs, and TEAEs that are associated with adjudicated arthropathy or sympathetic nerve system disorders (Adverse Events of Special Interest: AESIs) will be calculated for each treatment group.

Summary statistics will be calculated for values at each measurement time point as well as the changes from baseline therein for each treatment group for the clinical laboratory test parameters, body weight, vital signs (body temperature, sitting blood pressure, pulse rate), ECG parameters (heart rate, RR, PR, QRS, QT), and bone density. For urinalysis parameters, shift tables will be prepared for each treatment group, measurement time point, and category.

The numbers and proportions of subjects will be calculated for each treatment group, measurement time point, and category for the presence or absence of pain, the survey of autonomic symptoms (SAS) symptom score (1 or 2) and impact score (1 to 5), and the 3-level assessments of the neurological evaluation (cranial nerves, motor system, sensory system, reflexes, and coordination/balance).

The analysis methods used for the other safety endpoints will be described in the SAP.

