1. INTRODUCTION

This statistical analysis plan (SAP) is based on the final protocol (v4.0) dated 31-July-2018. This protocol will plan to respectively perform the statistical analysis for the clinical trial data from screening to Week 16, from screening to Week 24 and from screening to Week 68.

For the clinical trial data from screening to Week 68, this SAP covers statistical analysis, tabulations and listings of the study data to investigate the efficacy and safety of MT-5547 SC 1mg q4w and 1mg q8w compared to matching placebo. Therefore, this SAP will be finalized prior to database lock at Week 68 to ensure the credibility of the study results by pre-specifying the statistical methods for the data analyses before un-blinding of treatment assignments. For the clinical trial data from screening to Week 16 and from screening to Week 24 was separately created.

Any statistical analysis details described in this document supersede any description of statistical analysis in the protocol.

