6. STATISTICAL CONSIDERATIONS

6.1. Descriptive Statistics

(1) Non-PK related

Continuous data will be summarized descriptively using the number in the analysis set (N), the number of observations (n), mean, standard deviation (SD), median, minimum and maximum. Categorical data will be summarized using frequency counts and percentages. The denominator for the percentages will be the total number of subjects in the treatment group and analysis population being presented, unless otherwise specified.

(2) PK related

Serum concentrations will be summarized descriptively using N, n, mean, SD, median, Q1, Q3, minimum and maximum by clinical study day (as defined in the protocol) and treatment group.

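### The Week 68 SAP drops the protocol's counts by category for the autonomic symptom survey, keeps only two totals, and declares no change

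*SAP*

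**What the plan says.** Protocol 13.3.3 (Safety) states: "The numbers and proportions of subjects will be calculated for each treatment group, measurement time point, and category for the presence or absence of pain". That sentence also lists "the survey of autonomic symptoms (SAS) symptom score (1 or 2) and impact score (1 to 5") among the variables to be tabulated this way.

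The answer codes come from protocol 9.2.4.1.7. For symptoms, "The symptom scores will be assessed using the following 2 categories (12 items for males and 11 items for females"), with 1 printed for Yes and 2 for No. For impact, "The impact scores will be assessed using the following 5 categories", from 1 (not at all) to 5 (a lot). That section also sets two thresholds that prompt an eligibility review: "If the total symptom score at screening and at baseline is 4 or more or the total impact score at screening is 12 or more".

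Section 8.3.10 of the Week 68 SAP plans: "Absolute values and changes from baseline will be summarized at each assessment time point by treatment group for the following tests". The two tests named are the total symptom score and the total impact score, and all data are to be listed. Section 6.1 says what a summary contains: "Continuous data will be summarized descriptively using the number in the analysis set (N), the number of observations (n), mean, standard deviation (SD), median, minimum". The largest value is reported too.

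On precedence, the Week 68 SAP's introduction says: "Any statistical analysis details described in this document supersede any description of statistical analysis in the protocol". Its section 10 reports no changes to the analysis from the protocol.

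**The concern.** A planned safety table has disappeared without being declared. The SAP takes precedence, so the protocol's counts by category will not be produced unless someone notices the gap. A reader who relies on section 10 would believe that the protocol's analysis was carried out. Protocol 13.4 allows the analysis to be amended before lock, but asks that the SAP and the study report give the reason. Section 10 gives none.

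The table carries information that totals do not. Protocol 11.2.2 names three sources for assessing sympathetic nerve disorders: adverse event reports, standing blood pressure and the autonomic symptom assessment. Under 11.2.2.1 and 11.2.2.2 an event is entered as sympathetic dysfunction only after a specialist diagnoses it. The survey is therefore the systematic patient-reported record of symptoms short of that diagnosis. A total does not say which symptom became more frequent, or in how many subjects.

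**Working it through.** **1. The two plans side by side.**

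| | Protocol 13.3.3 | Week 68 SAP 8.3.10 |
|---|---|---|
| Unit summarised | Answer category: symptom 1 or 2, impact 1 to 5 | Total symptom score, total impact score |
| Statistic | Number and proportion of subjects | N, n, mean, SD, median, minimum, maximum of value and change |
| Layout | Arm and time point | Arm and time point |
| Individual data | Not stated | Listed |

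The codes 1 or 2 and 1 to 5 are answers to single items; a total over 11 or 12 items could not be confined to them. The protocol's table is therefore at item level. No such table for this survey appears elsewhere in the Week 68 SAP, and the Week 16 SAP does not analyse the survey. The Week 24 SAP is not among the documents. Counts planned there would not cover later visits.

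**2. What totals cannot show (assumed numbers, for illustration).** Take 100 subjects per arm and count one point per symptom.

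- Mean alone: if all 100 subjects have 1 symptom, the mean is 100 × 1 / 100 = 1.0. If 10 subjects have 10 symptoms and 90 have none, it is 10 × 10 / 100 = 1.0. Subjects with 4 or more symptoms number 0 and 10. The median (1 against 0) and maximum (1 against 10), which the SAP also reports, would separate these arms.
- Every planned statistic: in each arm 10 of 100 subjects have exactly 1 symptom. In one arm it is the same symptom in all 10; in the other it is a different symptom in each. The mean is 10 × 1 / 100 = 0.1 in both, and the SD, median, minimum and maximum are identical. An item table would show 10% on one item against 1% on each of ten items.

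The second case is the information that the dropped table held.

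**3. How the totals are formed.** Neither the protocol text nor the SAPs define them. Two scoring rules can be tested against the threshold of 4 for symptoms.

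- Sum of the printed codes: men run from 12 × 1 = 12 (all symptoms) to 12 × 2 = 24 (none), women from 11 × 1 = 11 to 11 × 2 = 22. Each further Yes lowers the total by 1, and every subject is above 4.
- Count of Yes answers: 0 to 12 in men, 0 to 11 in women. Each further Yes raises the total by 1, and the threshold of 4 separates subjects.

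For impact, adding codes 1 to 5 over all items gives a minimum of 12 × 1 = 12 in men, already at the threshold of 12, and 11 × 1 = 11 in women. Both thresholds thus suggest that only reported symptoms are meant to contribute.

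**The case against.** The strongest reply is that little is lost. The SAP gives the median and range as well as the mean, and lists all data. The Week 68 analysis makes no formal tests (section 6.2). Sympathetic dysfunction is confirmed by a specialist for each patient, not read from a group table. The signal is also tabulated elsewhere in the Week 68 SAP: events of special interest (8.3.1), a predefined group of events related to sympathetic dysfunction (7.1.3.1), and orthostatic blood pressure and pulse (8.3.3.1, with criteria in Appendix 2). All of this stands and limits the consequence. It does not restore the counts or make section 10 correct.

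A reader might also infer from the printed coding that the total falls as symptoms appear, so that the safety signal would be reversed. The documents do not support that. No text says that the totals are sums of the printed codes. The protocol numbers other option lists in the same way, such as seriousness and outcome. The thresholds point to a count of Yes answers. The survey form itself is an attachment that is not shown and may carry the scoring rule. What remains is that the SAP neither states nor cites a rule.

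**Conclusion.** The point holds in a limited form. The Week 68 SAP replaces a table that the protocol planned, overrides the protocol in doing so, and wrongly reports no change. The size is one descriptive safety table, at item and category level, on one of three inputs to an adverse event of special interest. No primary or key secondary result is affected. The documents give no observed distribution or SD for this survey, so the numerical effect on the trial's data cannot be estimated, and the examples above are assumptions.

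The undefined totals are a minor matter of clarity. The sex difference is also small under a count of Yes answers: a subject with no symptoms scores 0 in either sex, and only the maxima (12 and 11) differ.

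**What to change.** In section 8.3.10 of the Week 68 SAP, restore the number and percentage of subjects by item, category, arm and visit, and keep the summaries of the two totals beside them. Correct section 10 accordingly. If the table is not restored, section 10 should state that it was dropped and why, as protocol 13.4 asks.

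As a minor clarification, cite the instrument's scoring rule for the two totals, including how an absent symptom counts. The printed 1 = Yes, 2 = No coding and the thresholds in protocol 9.2.4.1.7 must be reconciled with that rule. This review takes no position on the thresholds themselves.

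The cost is SAP wording and one descriptive table from data already collected.
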